9. ADVERSE EVENTS: LIST AND REPORTING REQUIREMENTS

Adverse event (AE) monitoring and reporting is a routine part of every clinical trial.

Serious Adverse Events (SAEs) are reported by the site Lead Investigator within 24 hours to the Clinical Trial Network Monitoring Office (CTNMO) Coordinating Center Manager

by email ([contact]) or by [contact]. The 24 hour paging number for the CTNMO Coordinating Center Manager is [contact], [name]. The CTNMO Manager is then responsible for reporting SAEs to the UAB IRB and protocol P.I. in accordance with study-specific requirements. SAEs occurring at CTNMO sites are reported to the UAB IRB as “non-UAB” events.

A Serious Adverse Event (SAE) is an AE that 1) results in patient hospitalization or prolongation of hospitalization; 2) results in persistent or significant disability or incapacity; 3) results in death; 4) is a cancer or congenital abnormality or 5) results in the development of drug dependence or abuse. An AE must be considered an SAE when the nature or severity of the event is not consistent with the current Investigator’s Brochure. CTNMO site SAEs must be reported by the CTNMO site Lead Investigator to the CTNMO Coordinating Center Manager by email or by fax. It is also the responsibility of the CTNMO site Lead Investigator to report SAEs to the CTNMO site IRB and to submit copies of that report to the CTNMO Coordinating Center Manager. It is the CTNMO Coordinating Center Manager’s responsibility to report the SAE to the appropriate regulatory agency and / or industry sponsor. This submission of IND Safety Reports will be cross referenced according to local regulations to Onyx Investigational Compound Number (IND) at the time of submission.

Comprehensive Adverse Events and Potential Risks List (CAEPR)

The Comprehensive Adverse Event and Potential Risks list (CAEPR) provides a single, complete list of reported and/or potential adverse events (AE) associated with an agent using a uniform presentation of events by body system. In addition to the comprehensive list, a subset, the Agent Specific Adverse Event List (ASAEL), appears in a separate column and is identified with bold and italicized text. This subset of AEs (the ASAEL) contains events that are considered ‘expected’ for expedited reporting purposes only. The CAEPR may not provide frequency data; if not, refer to the Investigator’s Brochure for this information.

Adverse Event Characteristics

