- CTCAE term (AE description) and grade: The descriptions and grading scales found in the revised NCI Common Terminology Criteria for Adverse Events (CTCAE) version 4.03 will be utilized for AE reporting. All appropriate treatment areas should have access to a copy of the CTCAE version 4.03.
- “Expectedness”: AEs can be ‘Unexpected’ or ‘Expected’ for expedited reporting purposes only. ‘Expected’ AEs (the ASAEL) are bold and italicized in the CAEPR.
- Attribution of the AE:
 - Definite – The AE *is clearly related* to the study treatment.
 - Probable – The AE *is likely related* to the study treatment.
 - Possible – The AE *may be related* to the study treatment.
 - Unlikely – The AE *is doubtfully related* to the study treatment.
 - Unrelated – The AE *is clearly NOT related* to the study treatment.

Expedited Adverse Event Reporting

Expedited AE reporting for this study must use the reporting procedures briefly outlined in the table below.

Expedited Reporting Guidelines – Reporting Requirements for Adverse Events that occur within 30 Days¹ of the Last dose of the Investigational Agent on Phase 2 and 3 Trials

	Grade 1	Grade 2	Grade 2	Grade 3		Grade 3		Grades 4 & 5 ²	Grades 4 & 5 ²
	Un-expected and Expected	Unexpected	Expected	Unexpected with Hospitalization	without Hospitalization	Expected with Hospitalization	without Hospitalization	Unexpected	Expected
Unrelated Unlikely	Not Required	Not Required	Not Required	10 Calendar Days	Not Required	10 Calendar Days	Not Required	10 Calendar Days	10 Calendar Days
Possible Probable Definite	Not Required	10 Calendar Days	Not Required	10 Calendar Days	10 Calendar Days	10 Calendar Days	Not Required	24-Hour; 5 Calendar Days	10 Calendar Days

¹ Adverse events with attribution of possible, probable, or definite that occur greater than 30 days after the last dose of treatment require reporting as follows:

24-hour notification followed by complete report within 5 calendar days for:

- Grade 4 and Grade 5 unexpected events

10 calendar day report:

- Grade 3 unexpected events with hospitalization or prolongation of hospitalization
- Grade 5 expected events

² Although a 24-hour notification is not required for death clearly related to progressive disease, a full report is required as outlined in the table.

Note: All deaths on study require both routine and expedited reporting regardless of causality. Attribution to treatment or other cause must be provided.

- Expedited AE reporting timelines defined:

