 - “24 hours; 5 calendar days” – The investigator must initially report the AE within 24 hours of learning of the event followed by a complete report within 5 calendar days of the initial 24-hour report.
 - “10 calendar days” - A complete report on the AE must be submitted within 10 calendar days of the investigator learning of the event.
- Any medical event equivalent to CTCAE grade 3, 4, or 5 that precipitates hospitalization (or prolongation of existing hospitalization) must be reported regardless of attribution and designation as expected or unexpected with the exception of any events identified as protocol-specific expedited adverse event reporting exclusions.
- Any event that results in persistent or significant disabilities/incapacities, congenital anomalies, or birth defects must be reported.
- Use the protocol number and the protocol-specific patient ID assigned during trial registration on all reports.

Expedited Reporting by Investigator to Onyx

The Investigator must inform Onyx in writing by e-mail or Fax at the contact information listed below of all Expedited Safety Reports submitted to the relevant health authorities (HA). **These notifications should be performed in parallel to the HA submissions [e.g., within 7 calendar days for any fatal or life-threatening suspected unexpected serious adverse reactions (SUSARs) and within 15 calendar days for all other SUSARs}, but in no case any later than 1 business day from the submission date. This must be documented on a FDA 3500a MEDWATCH or CIOMS I form. All other SAEs will be sent to Onyx within 30 days of the event on a FDA 3500a MEDWATCH, CIOMS I, or local SAE form. All forms must be completed and provided to Onyx in English.**

The initial report must be as complete as possible, at a minimum including the SAE term(s), patient identifier, date of awareness of the event, an investigator assessment of the causal relationship between the event and the Onyx product(s), and name of the investigator. Information not available at the time of the initial report (e.g., an end date for the SAE or laboratory values received after the report) must be documented on a follow-up form, and submitted to Onyx in the same timelines as outlined above. The Onyx protocol number (IST-CAR-612) and the institutional protocol number should be included on all SAE reports to Onyx.

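### Section 9 uses an expectedness test (inconsistency with the Investigator's Brochure) to define a serious adverse event, so mild unlisted events become SAEs

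*Combined protocol and SAP*

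**What the plan says.** The opening of Section 9 sets the duty that follows from SAE status: "Serious Adverse Events (SAEs) are reported by the site Lead Investigator within 24 hours", with the coordinating center as recipient. The definition begins "A Serious Adverse Event (SAE) is an AE that 1) results in patient hospitalization or prolongation of hospitalization" and goes on to disability, death, cancer or congenital abnormality, and drug dependence or abuse. The next sentence reads "An AE must be considered an SAE when the nature or severity of the event is not consistent with the current" Investigator's Brochure.

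The CAEPR paragraph then gives a different source for expectedness. Of the Agent Specific Adverse Event List it says "This subset of AEs (the ASAEL) contains events that are considered" expected, and it limits that label: "for expedited reporting purposes only. The CAEPR may not provide frequency data". It sends the reader to the Brochure only for frequencies. Under Adverse Event Characteristics the source is repeated: "the ASAEL) are bold and italicized in the CAEPR".

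The Expedited Reporting table is mandatory. It sorts events by grade, expectedness and attribution, and at Grade 3 also by hospitalization. The subsection on reporting to the drug supplier gives 7 days for fatal or life-threatening SUSARs "and within 15 calendar days for all other SUSARs", and 30 days for other SAEs.

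**The concern.** Seriousness concerns what happened to the patient. Expectedness concerns whether the reference safety document foresaw the event. The added sentence makes the second sufficient for the first. A transient mild symptom that the Brochure does not list would be classed with hospitalizations and deaths, and its class could change when the Brochure is revised, which Section 14 anticipates.

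The practical stake is the safety-reporting channel. A site following the definition must give 24-hour notice of events that the table, a few paragraphs later, does not ask it to report at all. Because the definition and the table use different reference documents, two sites could also classify the same event differently.

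**Working it through.** The plan gives no figure to reproduce on this point. The check is a comparison of texts and a count of table cells.

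**Step 1. What the sentence requires.** It is mandatory. It has one condition, that the event departs from the Brochure in kind or in severity. It sets no minimum grade, refers to none of the five outcomes and does not ask about causality. Nothing elsewhere in the document limits it.

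**Step 2. How the rest of the document treats the two properties.** It keeps them apart. The reporting table gives expectedness and hospitalization separate places. The line listing of SAEs for the supplier asks for an expectedness assessment on each SAE. Section 14 speaks of events that are serious, unexpected or both when it describes notice to the IRB.

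**Step 3. The table for unexpected events.** Grade 1 is a single column that covers expected and unexpected events.

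| Unexpected event | Unrelated or unlikely | Possible, probable or definite |
|---|---|---|
| Grade 1 | none | none |
| Grade 2 | none | 10 days |
| Grade 3, hospitalized | 10 days | 10 days |
| Grade 3, not hospitalized | none | 10 days |
| Grades 4 and 5 | 10 days | 24 hours, then 5 days |

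Five rows by two attribution columns give 10 cells: 4 with no expedited report, 5 with a 10-day report and 1 with a 24-hour report (4 + 5 + 1 = 10). Under the added sentence, an event in any of the 10 cells that also departs from the Brochure is an SAE with 24-hour notice to the coordinating center. The table itself has a 24-hour duty in only 1 of the 10.

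**Step 4. The supplier route.** A SUSAR must be suspected to be related, unexpected and serious. A mild unlisted event that is suspected to be related gets its seriousness from the added sentence and so fits the wording. A mild unlisted event judged unrelated becomes an SAE but not a SUSAR, and falls under the text for other SAEs.

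**Step 5. Source of expectedness.** The definition uses the Brochure and the table uses the ASAEL. The SUSAR text names neither. An event could therefore be unexpected by one source and expected by the other.

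**Step 6. What the sentence does at present for life-threatening events.** The five outcomes do not include life-threatening events, although the SUSAR text relies on that category. A life-threatening event with none of the five outcomes is now an SAE only if it departs from the Brochure. If it is consistent with the Brochure, it is not an SAE even under the current text. The Grade 4 and 5 cells of the table cover this only in part, since they set report times and do not confer SAE status.

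**The case against.** The strongest reply is that the sentence is a cautious internal trigger. The 24-hour rule is addressed to the coordinating center, while the table names no recipient, so the two may be separate channels with separate clocks. Any error is then over-reporting, not missed harm. This stands in part: it may ease the clash in timing. It does not remove the misclassification, because the sentence changes what an event is called and not merely who hears of it.

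Several stronger readings are tempting and are not supported:

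- A reader might infer that the toxicity endpoint is distorted. The objective is stated only as toxicities. Section 10 grades them by CTCAE version 4.03, mentions no SAE count and plans no comparison with the SAE rate of 26 of 47 patients (55.3%) quoted in Section 1.3. A CTCAE grade does not change with SAE status.
- A reader might add an assumed share of patients with unlisted mild events to that 55.3% and report an inflated SAE rate. The documents give no basis for such a share. It would depend on what the Brochure lists, and the 47 patients belong to another study.
- A reader might infer that every mild unlisted event becomes a SUSAR. Suspected relatedness is also needed. In addition, the supplier text ties its timelines to reports sent to health authorities and gives them as examples, and Section 14 commits the trial to FDA and ICH requirements. Whether the added sentence governs those submissions is an inference.
- A reader might infer that the Brochure and the ASAEL actually disagree. Neither list is available here, so disagreement is possible but not shown.
- A reader might call the limit of expectedness to expedited reporting a flat self-contradiction. That limit governs the ASAEL labels. It sits badly beside the added sentence but does not by itself contradict it.

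**Conclusion.** The point holds as a defect in the SAE definition. A mandatory sentence makes unexpectedness by the Brochure sufficient for seriousness, against the way the rest of Section 9 and Section 14 use the two terms. Read literally, it places Grade 1 and 2 unlisted events in the 24-hour SAE channel, and in the SUSAR wording if they are suspected to be related. The table asks for no expedited report in 4 of its 10 unexpected-event cells and draws expectedness from another source.

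The effect is limited to SAE classification and reporting load. The primary endpoint, the sample size, the decision rule and the CTCAE-graded toxicity analysis are unaffected, and no numerical inflation can be derived from the documents. The conclusion rests on a literal reading of the sentence and on no assumed rate. It should be corrected, since the correction is cheap and sites cannot now apply one consistent rule.

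**What to change.** Make three changes to Section 9 in one edit.

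1. Reword the added sentence so that an AE departing from the Brochure in kind or severity is called unexpected, not serious.
2. Reconcile the outcome list in the SAE definition with the life-threatening category in the supplier reporting text, so that no life-threatening event loses SAE status. The first change should not be made without this one: for a life-threatening event with none of the five outcomes, the sentence being reworded is now the only route to SAE status.
3. Name one reference document for expectedness, to serve both the expedited table and SUSARs, and revise the CAEPR paragraph and the expectedness bullet under Adverse Event Characteristics to match.

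The cost is a few sentences of text in one section. No new data are collected and no analysis changes. Sites would have fewer mild events to report within 24 hours.

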10. STATISTICAL CONSIDERATIONS

Study Design/Endpoints

This is a 2-center one-stage non-randomized phase II trial conducted at UAB Comprehensive Cancer Center and outside sites. Clinical PFS as the primary end-point and the trial will enroll 28 patients. The eligible population includes men with metastatic CRPC who have received prior abiraterone and/or enzalutamide (prior chemotherapy and sipuleucel-T are allowed). Therapy will continue until progression (as defined below) or severe toxicities. Patients removed for reasons other than progression will continue to be followed until progression or initiation of another agent. Correlative studies include serial CTC enumeration (day 1 of cycles 1, 2 and cycle 4) and collection of whole blood is performed at baseline for 20S proteasome activity. Progression of disease will be defined clinically as the first occurrence of any of the following, and PSA progression alone will not constitute progression:

- 1) Two distinct new lesions on bone scan consistent with bone metastases in the best judgment of the investigator and confirmed by further new lesions on a subsequent scan ≥ 6 weeks later.
- 2) Progression in measurable disease as defined by RECIST criteria
- 3) Worsening of pain in the judgment of the investigator.
- 4) New bladder outlet or ureteral obstruction caused by cancer

- 5) New bone related events
 - a. Pathologic fracture
 - b. Spinal cord compression
 - c. Need for palliative radiation, surgery, or kyphoplasty to any neoplastic bone lesion
- 6) Deterioration of performance status to ECOG level 3-4
- 7) Death

Modest activity is considered clinically meaningful in this relatively heavily pretreated population with metastatic CRPC that has received abiraterone acetate and/or enzalutamide (prior chemotherapy and sipuleucel-T are allowed). The null hypothesis for this trial is that the primary endpoint of 6-month PFS <10% is not clinically meaningful and the alternative hypothesis is that the true clinical PFS of interest is $\geq 30\%$. Since we will follow all subjects for at least 6 months or until progression or death, we will not have censoring and 6 months PFS can be treated as a binomial random variable. With twenty five evaluable patients we will have 80% power for an exact binomial test at the one sided 0.05 significance level of the null hypothesis that the 6-month PFS rate is 10% if the actual rate is 30%. That null hypothesis will be rejected if 6 or more of the 25 subjects survive for 6 months progression free. Twenty-eight subjects will be accrued to allow for 10% inevaluable patients.

Sample Size/Accrual Rate

A total of 28 patients will be enrolled for this trial. Accrual period will be 6 to 12 months.

Analysis of Secondary Endpoints

The Kaplan-Meier method will be used to estimate PFS and OS rates over time with standard errors estimated using Greenwood's formula. Medians and their 95% confidence intervals will also be estimated. PSA response, PSA decline $\geq 30\%$ within 3 months, RECIST responses and regressions, pain response and CTC alterations will be analyzed as secondary endpoints. CTC changes will include changes from unfavorable ($\leq 5/7.5\text{ml}$) to favorable, and declines by $>30\%$. Pain response is defined as decline in present pain index ≥ 2 points and/or decrease in analgesics. Linear regression with PSA as the dependent variable and time as the dependent variable will be performed and used to estimate PSA DT. The association of baseline whole blood 20S proteasome level with PFS and other secondary endpoints will be examined using Cox regression to generate hypotheses for selecting suitable patients for further study.

Reporting and Exclusions

All patients will be evaluable for toxicity from the time of their first treatment with carfilzomib. CTCAE v 4.03 will be utilized to grade toxicities (Appendix). All patients included in the study will be assessed for response to treatment, even if there are major protocol treatment deviations or if they are ineligible. Each patient will be assigned one of the following categories: 1) complete response, 2) partial response, 3) stable disease, 4) progressive disease, 5) early death from malignant disease, 6) early death from toxicity, 7) early death because of other cause, or 9) unknown (not assessable, insufficient data). [Note: By arbitrary convention, category 9 usually designates the "unknown"]

status of any type of data in a clinical database.]

All of the patients who met the eligibility criteria (with the possible exception of those who received no study medication) should be included in the main analysis of the response rate. Patients in response categories 4-9 should be considered to have a treatment failure (disease progression). Thus, an incorrect treatment schedule or drug administration does not result in exclusion from the analysis of the response rate. Precise definitions for categories 4-9 will be protocol specific.

All conclusions should be based on all eligible patients. Sub-analyses may then be performed on the basis of a subset of patients, excluding those for whom major protocol deviations have been identified (e.g., early death due to other reasons, early discontinuation of treatment, major protocol violations, etc.). However, these sub-analyses will not serve as the basis for drawing conclusions concerning treatment efficacy, and the reasons for excluding patients from the analysis will be clearly reported. The 95% confidence intervals should also be provided.

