The choice of a primary endpoint in metastatic CRPC is difficult as this disease is characterized by a poor ability to measure response and PFS, the typical primary endpoints in phase II trials. Measurable lesions by RECIST are seldom observed, since the most common site of metastases is bone, a non-measurable site [26]. Although, a $\geq 30\%$ or $\geq 50\%$ PSA decline within 3 months and time to clinical progression may be useful surrogates for long-term outcomes with chemotherapeutic agents, its validity with biological agents is unknown [27-29]. Regression of measurable tumor was associated with survival in one study, but external validation is required and measurable tumors are found in the minority of patients. Prostate Cancer Working Group (PCWG)-2 guidelines recommend time to event primary endpoints rather than response endpoints [27]. Moreover, an early switch in therapy within 3 months was discouraged due to the poor reliability of early changes in PSA and bone scans. Vaccines may potentially induce a transient rise in PSA as well as increases in size of measurable lesions by provoking an immune reaction in the normal and malignant prostate tissue. Guidelines have been recommended to standardize methodology used for the calculation and employment of PSA doubling time changes to provide a signal of activity in early trials [30].

Changes in CTCs (circulating tumor cells) appear promising as prognostic factors in the setting of chemotherapy and abiraterone, but require validation in the context of biologic agents [31, 32]. Moreover, it is unclear if unfavorable CTC alterations can be utilized to switch therapy. CTC is emerging as a highly important prognostic marker for metastatic CRPC and appears better than PSA. In one prospective trial, blood was drawn from CRPC patients with progressive disease starting a new line of chemotherapy before

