2. Progression in measurable disease as defined by RECIST 1.1 criteria
3. Worsening of pain (increase in present pain index by ≥ 1 point, increased need for analgesics).
4. New bladder outlet or ureteral obstruction caused by cancer
5. New bone related events
 - a) Pathologic fracture
 - b) Spinal cord compression
 - c) Need for palliative radiation, surgery, or kyphoplasty to any neoplastic bone lesion
6. Deterioration of performance status to ECOG level 3-4

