11. MEASUREMENT OF EFFECT

Antitumor Effect

For the purposes of this study, patients should be re-evaluated for response every 12 weeks and earlier if clinically required. Response and progression will be evaluated in this study using the new international criteria proposed by the Response Evaluation Criteria in Solid Tumors (RECIST 1.1)[26]. Changes in only the largest diameter (unidimensional measurement) of the tumor lesions are used in the RECIST criteria.

All patients will be evaluable for toxicity from the time of their first treatment with Carfilzomib. Only those patients who have measurable disease present at baseline, have received at least one cycle of therapy, and have had their disease re-evaluated will be considered evaluable for response. These patients will have their response classified according to the definitions stated below. (Note: Patients who exhibit objective disease progression prior to the end of cycle 1 will also be considered evaluable.)

Measurable disease. Measurable lesions are defined as those that can be accurately measured in at least one dimension (longest diameter to be recorded) as ≥ 20 mm with conventional techniques (CT, MRI, x-ray) or as ≥ 10 mm with spiral CT scan. Lymph nodes are considered measurable if the short axis diameter is ≥ 15 mm. All tumor measurements must be recorded in millimeters (or decimal fractions of centimeters). Tumor lesions that are situated in a previously irradiated area might or might not be considered measurable

Non-measurable disease. All other lesions (or sites of disease), including small lesions (longest diameter < 20 mm with conventional techniques or < 10 mm using spiral CT scan), are considered non-measurable disease. Bone lesions, leptomeningeal disease, ascites, pleural/pericardial effusions, lymphangitis cutis/pulmonis, inflammatory breast disease, abdominal masses (not followed by CT or MRI), and cystic lesions are all non-measurable.

Bone disease: According to PCWG-2 guidelines, 2 distinct new lesions on bone scan consistent with bone metastases in the best judgment of the investigator and confirmed by further new lesions on a subsequent scan ≥ 6 weeks later is defined as bone scan progression.

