Ultrasound (US) should not be used to measure tumor lesions. It is, however, a possible alternative to clinical measurements of superficial palpable lymph nodes, subcutaneous lesions, and thyroid nodules. US might also be useful to confirm the complete disappearance of superficial lesions usually assessed by clinical examination.

The utilization of endoscopy techniques for objective tumor evaluation has not yet been fully and widely validated. Their uses in this specific context require sophisticated

equipment and a high level of expertise that may only be available in some centers. Therefore, the utilization of such techniques for objective tumor response should be restricted to validation purposes in reference centers. However, such techniques may be useful to confirm complete pathological response when biopsies are obtained.

Tumor markers alone cannot be used to assess response. If markers are initially above the upper normal limit, they must normalize for a patient to be considered in complete clinical response. Specific additional criteria for standardized usage of prostate-specific antigen (PSA) and CA-125 response in support of clinical trials are being developed.

The cytological confirmation of the neoplastic origin of any effusion that appears or worsens during treatment when the measurable tumor has met criteria for response or stable disease is mandatory to differentiate between response or stable disease (an effusion may be a side effect of the treatment) and progressive disease.

Response Criteria for the evaluation of Target Lesions

Complete Response (CR): Disappearance of all target lesions

Partial Response (PR): At least a 30% decrease in the sum of the longest diameter (LD) of target lesions, taking as reference the baseline sum LD

Progressive Disease (PD): At least a 20% increase in the sum of the LD of target lesions, taking as reference the smallest sum LD recorded since the treatment started or the appearance of one or more new lesions

Stable Disease (SD): Neither sufficient shrinkage to qualify for PR nor sufficient increase to qualify for PD, taking as reference the smallest sum LD since the treatment started

Evaluation of Non-Target Lesions

Complete Response (CR): Disappearance of all non-target lesions and normalization of tumor marker level

Note: If tumor markers are initially above the upper normal limit, they must normalize for a patient to be considered in complete clinical response.

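### The primary-endpoint event list limits soft-tissue progression to measurable disease, Section 11 does not, and the plan leaves it contradictory which rule applies to patients without measurable disease at baseline

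*Combined protocol and SAP*

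**What the plan says.** Section 10 (Study Design/Endpoints) defines progression by a closed list, and whichever item happens first is the event. Two items rest on imaging. Item 1 is bone scan: "Two distinct new lesions on bone scan consistent with bone metastases in the best judgment of the investigator", with later confirmation by further new lesions. Item 2 is soft tissue: "Progression in measurable disease as defined by RECIST criteria". The Synopsis and Section 6.3 word item 2 identically. Section 3.1 adds only the version number: "Progression in measurable disease as defined by RECIST 1.1 criteria". No list has a separate item for new soft-tissue lesions or for worsening of non-measurable soft-tissue disease.

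Section 11 is broader. It begins "Response and progression will be evaluated in this study using the new international criteria proposed by the" RECIST 1.1 group. Its target-lesion criterion for progressive disease ends "or the appearance of one or more new lesions". Its non-target criterion counts new lesions and clear worsening of existing non-target lesions, and its overall-response table gives progressive disease for any new lesion, whatever the target and non-target status. The same section also limits who is evaluable for response: "Only those patients who have measurable disease present at baseline, have received at least one cycle of therapy, and have had their disease re-evaluated". It then says that these patients have their response classified by the definitions that follow.

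Section 4.1 requires metastatic disease but not measurable disease. Section 1.1 states: "Measurable lesions by RECIST are seldom observed, since the most common site of metastases is bone, a non-measurable site". The study calendar (Section 8) schedules CT of chest, abdomen and pelvis at baseline and every 3 cycles for all patients on study. Section 11 defines PFS as time from start of treatment to progression or death and sets no condition on measurability.

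**The concern.** By the protocol's own account, most patients will enter without measurable disease. Read literally, item 2 gives such a patient nothing in soft tissue that can progress, unless a new lesion is large enough to be measurable in its own right. A growing node still below the 15 mm short axis, a malignant effusion or clear worsening of other non-target disease then matches no item until pain, obstruction, a skeletal event, ECOG 3-4 or death follows. Read through Section 11, the same finding is progressive disease.

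Two sites could therefore classify the same CT differently, and both could cite the protocol. The endpoint is a yes/no count in 25 patients with a cut-off of 6, so a few differently classified patients can decide the trial. Under the literal reading, patients with soft-tissue progression would be counted as successes.

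**Working it through.** **Step 1. The passages side by side.**

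| Finding in a patient without measurable disease at baseline | Item 2, literal | Section 11 |
|---|---|---|
| Clear worsening of non-target soft-tissue disease | Not an event | Progressive disease |
| New soft-tissue lesion too small to be measurable | Not an event | Progressive disease |
| New soft-tissue lesion large enough to be measurable | Arguable | Progressive disease |
| Two new bone-scan lesions, confirmed later | Event (item 1) | Event (bone disease paragraph) |

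The first two rows contradict each other and the third is unclear. The evaluability sentence in Section 11 does not settle the matter. It is written for response, but the definitions of progressive disease follow directly under it. Nor can Section 11 be carried over whole: it calls one new lesion progression, whereas item 1 needs two new bone lesions and confirmation.

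**Step 2. The plan's own figures.** Inputs from Section 10: n = 25 evaluable, null rate 10%, alternative 30%, one-sided 0.05, reject at 6 or more, 28 enrolled for 10% inevaluable.

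P(X ≥ 6 | 25, p) = 1 − Σ(k = 0 to 5) C(25,k) p^k (1−p)^(25−k)

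- p = 0.10: 0.0334 (size)
- p = 0.30: 0.8065 (stated power 80%)
- Cut-off 5 instead of 6: size 0.0980, so 6 is the correct cut-off
- 25 / 0.90 = 27.8, rounded up to 28

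The stated design reproduces. This point does not show any stated figure to be wrong.

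**Step 3. Sensitivity to misclassification.** Let m be the share of all patients who have progressed by 6 months on the broader definition but are counted as progression-free only because of the literal reading of item 2. The documents give no value for m, so it is an assumption. If the 10% null refers to the broader definition, the apparent null rate is 0.10 + m.

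| m (assumed) | Apparent null rate | P(X ≥ 6 of 25) |
|---|---|---|
| 0 | 0.10 | 0.0334 |
| 1% | 0.11 | 0.0499 |
| 2% | 0.12 | 0.0709 |
| 4% (1 in 25) | 0.14 | 0.1268 |
| 5% | 0.15 | 0.1615 |
| 10% | 0.20 | 0.3833 |

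The size equals 0.05 at an apparent rate of 0.1101, so m is about 1.0%.

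**Step 4. The same thing built from two shares.** Let a be the share of patients without measurable disease and v the share of their failures that are soft-tissue-only. Then m = 0.90 × a × v. With a = 60% (assumed):

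- v = 1%: 0.10 + 0.90 × 0.6 × 0.01 = 0.1054, size 0.042
- v = 5%: 0.127, size 0.088
- v = 10%: 0.154, size 0.177
- v = 20%: 0.208, size 0.423

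The 0.05 limit is crossed at v = 0.0101 / (0.90 × 0.6), about 1.9%. For a small v the size stays below 0.05.

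**The case against.** The strongest reply is that Section 11 already supplies the rule. Item 2 defers to RECIST, Section 11 applies RECIST 1.1 to progression without restriction, and its text makes any new lesion progressive disease. The evaluability sentence concerns response, and the PFS definition carries no such condition. Section 10 (Reporting and Exclusions) assigns every patient a category that includes progressive disease, although that text concerns the response rate. Much of this stands, and it rules out treating the literal reading as the plan's settled meaning. It does not remove the conflict, because item 2 still carries a qualifier that would be unnecessary if any RECIST progression were meant.

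A second reply concerns size. Section 10 states the 10% null directly after its event list and cites no benchmark that uses a broader definition. If the 10% was set for PFS as listed, the literal reading inflates nothing. This stands, and the figures in Steps 3 and 4 are conditional on the other case. To count toward v, a failure must also show none of the other listed events by 6 months, so v may be small.

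A reader might infer three stronger claims that the documents do not support:

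- That no imaging progression counts without measurable disease. Confirmed new bone-scan lesions count under item 1, and bone is the commonest site.
- That a patient with a new liver or nodal metastasis is definitely progression-free under the plan. Section 11 says otherwise, and a large enough new lesion is itself measurable by Section 11's definition.
- That such a patient necessarily stays on treatment. Section 6.3 also allows therapy to stop for changes in condition, in the investigator's judgement.

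**Conclusion.** The concern holds as a contradiction within the primary-endpoint rule. Item 2 and Section 11 give different answers for non-measurable or non-target soft-tissue worsening in patients without measurable disease at baseline, and these patients are the majority by the protocol's own account.

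Its size cannot be derived from the documents. If the 10% null refers to PFS that counts these events, the design has little room: about 1% of patients misclassified uses up the gap between 0.033 and 0.05, and 4% gives 0.127. A reader might conclude that the type I error is in fact inflated. That would need both a null rate set on the broader definition and a misclassified share, and the documents establish neither.

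**What to change.** In Section 10, reword item 2 for the primary endpoint so that soft-tissue progression by RECIST 1.1 (target lesions, non-target lesions or any new soft-tissue lesion) is a PFS event whether or not measurable disease was present at baseline. Keep bone lesions under item 1. In Section 11, state that the measurable-disease condition limits the response rate only and not the assessment of progression.

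The matching lists in the Synopsis, Section 3.1 and Section 6.3 also govern how long therapy continues. The sponsor must reconcile them with the endpoint definition. This review does not propose a rule for stopping treatment.

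The cost is wording. No scans are added, and n = 25, the cut-off of 6 and the enrolment of 28 are unchanged. The observed 6-month PFS rate may be slightly lower. The plan should also say which event definition the 10% and 30% rates refer to. If they were set on the narrower list, counting more events costs power: with an assumed 4% of patients affected, P(X ≥ 6 | 25, 0.26) = 0.664 against 0.807 as planned.
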